4.3.1.2.5 Duration

Duration is derived from the start and end dates of the unsolicited AE:

Duration = End date of unsolicited AE - start date of unsolicited AE + 1.

The duration is considered as missing only if one or both of the start and end dates of the unsolicited AE is missing or partially missing.

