9.2.3.3 Unsolicited Adverse Events

In addition to recording solicited reactions, subjects will be instructed to record any other medical events that may occur during the 30-day period after vaccination. Space will be provided in the diary card for this purpose.

Information on SAEs will be collected and assessed throughout the study, from the time of vaccination until 30 days (+14 days) after vaccination. Any SAE occurring at any time during the study will be reported by the Investigator in the CRB according to the completion instructions provided by the Sponsor; this includes checking the “Serious” box on the AE CRF and completing the appropriate Safety Complementary Information CRFs. All information concerning the SAE is to be reported either as part of the initial reporting or during follow-up reporting if relevant information became available later (eg, outcome, medical history, results of investigations, copy of hospitalization reports).

For each unsolicited AE (whether serious or non-serious), the following information is to be recorded:

- Start and stop dates^a
- Intensity of the event:

For measurable unsolicited AEs that are part of the list of solicited reactions, the size of the AE as well as the temperature for fever will be collected and analyzed based on the corresponding scale used for solicited reactions (see [Table 9.1](#) and [Table 9.2](#)).

All other unsolicited AEs will be classified according to the following intensity scale:

- Grade 1: A type of adverse event that is usually transient and may require only minimal treatment or therapeutic intervention. The event does not generally interfere with usual activities of daily living.
- Grade 2: A type of adverse event that is usually alleviated with additional therapeutic intervention. The event interferes with usual activities of daily living, causing discomfort but poses no significant or permanent risk of harm to the research participant.

^a The stop date of all related AEs will be actively solicited. For other events, the investigator will provide the stop date when it becomes available. AEs for which no stop date was obtained during the course of the study will be considered as ongoing at the end of the study.

- Grade 3: A type of adverse event that interrupts usual activities of daily living, or significantly affects clinical status, or may require intensive therapeutic intervention.
- Whether the AE was related to the investigational product (for unsolicited systemic AEs)

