4.3.1.1.6 Overall Number of Days of Occurrence

If a reaction is ongoing at the end of the solicited period, then the overall number of days of occurrence is derived from the daily intensities and the end date of the reaction after the end of the solicited period.

The overall number of days of presence is:

$$\begin{aligned} & (\text{End date} - \text{last vaccination date}) + (\text{number of days of occurrence within the solicited period}) \\ & - \text{length of the solicited period} + 1 \end{aligned}$$

If the end date is missing or incomplete (contains missing data), the overall number of days of occurrence will be considered as Missing.

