4.3.1.1.7 Ongoing

Ongoing is derived from the last daily intensity of the solicited period computed as described in [Section 4.3.1.1.1](#) and the maximum intensity on the ongoing period. The investigator's ongoing flag is not used because the measurement would determine the ongoing status of the reaction.

- Ongoing: if the last daily intensity of the solicited period is at least Grade 1 and the maximum intensity on the ongoing period is at least Grade 1
- Not ongoing: if the last daily intensity of the solicited period is None or the maximum intensity on the ongoing period is None.
- Missing: all other conditions (in this case, it is not included in the denominator of the ongoing analysis in the safety tables).

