5.3.1.4 Start Date and End Date

Missing or partially missing start dates or end dates for unsolicited AEs (including SAEs) will remain missing and not be imputed. If the start date is missing or partially missing, the time of onset will be considered to be missing. Nevertheless unsolicited AEs with missing time of onset will be included in analyses according to the last vaccination (computed according to the [Section 4.3.1.2.3](#)). If either the start date or end date is missing or partially missing, the duration will be considered missing.

Missing or partially missing end dates for ongoing solicited AEs will remain missing and not be imputed.

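### Unsolicited AEs without an end date count as ongoing in the protocol but get a missing duration in the SAP, so duration summaries limited to events with an end date tend to read short

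*SAP*

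**What the plan says.** Duration is a listed endpoint for unsolicited AEs and for SAEs in both documents (Protocol 9.2.2, SAP 4.2).

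- **Derivation.** SAP 4.3.1.2.5: "Duration = End date of unsolicited AE - start date of unsolicited AE + 1".
- **Missing dates.** The same section adds: "The duration is considered as missing only if one or both of the start and end dates of the unsolicited AE is missing" or partially so. SAP 5.3.1.4 repeats it ("If either the start date or end date is missing or partially missing, the duration will be considered missing") and rules out filling in dates: "Missing or partially missing start dates or end dates for unsolicited AEs (including SAEs) will remain missing and not be imputed".
- **Meaning of an absent stop date.** A footnote to Protocol 9.2.3.3: "AEs for which no stop date was obtained during the course of the study will be considered as ongoing at the end of the study". It also says that stop dates of related AEs are actively sought, while for other events the investigator supplies the date if and when it is available.
- **Solicited reactions continuing past Day 7.** SAP 4.3.1.1.6 has a parallel rule: "If the end date is missing or incomplete (contains missing data), the overall number of days of occurrence will be considered as Missing".

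The SAP defines an ongoing status only for solicited reactions (4.3.1.1.7). Unsolicited AEs have no such status, no censoring at last contact and no *at least x days* display.

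**The concern.** An event still ongoing at last contact does not have an unknown duration. It is right-censored: it lasted at least from its start to last contact. Coding it as missing discards that information and puts it in the same class as an event whose end date was lost or only partly recorded.

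The loss is selective. Whether an end date exists by Visit 2 depends on how long the event lasted, so long events lose their duration more often than short ones. At stake is a descriptive safety endpoint in a trial whose stated safety purpose is to describe the vaccine's safety profile. A reader given durations for resolved events only, with no count of unresolved ones, would think AEs shorter than they were.

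**Working it through.** **No plan figure to reproduce.** The documents give no duration distribution, no expected share of AEs without a stop date and no planned duration statistic. The check is therefore of direction, then of size under stated assumptions.

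**Inputs from the documents**
- Visit 2 falls on Day 30 to Day 44 (Protocol 5.1.3).
- Analysed unsolicited AEs start on Day 0 to Day 30 (SAP 4.3.1.2.4).
- Duration is end − start + 1 (SAP 4.3.1.2.5).

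**Direction.** Let D be the true duration and C = last contact − start + 1. Without a later stop date, D is recorded only if D ≤ C. If D and C are independent, P(D ≤ d | D ≤ C) ≥ P(D ≤ d) for every d, so recorded durations are stochastically shorter than true ones. The longest recordable duration is 30 − 0 + 1 = 31 days with Visit 2 on Day 30 and 44 − 0 + 1 = 45 days with Visit 2 on Day 44. It is less for later onsets.

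**Size: assumptions (not in the documents).** Onset uniform on Days 0–30; Visit 2 uniform on Days 30–44; duration exponential with mean m, rounded up to whole days; no stop date recovered after Visit 2.

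- True mean = 1/(1 − e^(−1/m)). For m = 7 this is 7.51 days.
- Share lost = average of e^(−(V − o + 1)/m) over onset day o and visit day V. For m = 7 it is the product of the average of e^(o/7), 17.395; the average of e^(−V/7), 0.006084; and e^(−1/7), 0.8669. That gives 0.0917.

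| m (days) | True mean | Durations lost | Mean of events with an end date | Ratio |
|---|---|---|---|---|
| 3 | 3.5 | 2% | 3.4 | 0.97 |
| 7 | 7.5 | 9% | 6.3 | 0.84 |
| 14 | 14.5 | 25% | 9.1 | 0.63 |

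**Half of the late stop dates recovered.** The mean true duration of the lost events is (true mean − kept share × kept mean) / lost share.
- m = 7: (7.512 − 0.9083 × 6.334)/0.0917 = 19.2 days. With half recovered: (0.9083 × 6.334 + 0.0459 × 19.2)/0.9541 = 7.0 days.
- m = 14: (14.506 − 0.7532 × 9.135)/0.2468 = 30.9 days. With half recovered: (0.7532 × 9.135 + 0.1234 × 30.9)/0.8766 = 12.2 days.

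**Sensitivity to visit day and distribution.** With last contact fixed at Day 30 or Day 44, exponential or log-normal (sigma 1) durations and nothing recovered, the ratio of recorded to true mean is:
- true mean 3.5 days: 0.86–0.91 (Day 30), 0.96–1.00 (Day 44);
- true mean 7.5 days: 0.70–0.75 (Day 30), 0.85–0.92 (Day 44);
- true mean 14.5 days: 0.53 (Day 30), 0.68–0.72 (Day 44).

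Across all scenarios tried, including a mean of 30 days, the ratio ran from 0.31 to 1.00. It rose to 0.78–1.00 if half of all AEs always receive a stop date. The direction never reversed.

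**The case against.** Several counter-arguments limit the point.

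- **The no-recovery scenario is a worst case.** Stop dates of related AEs are actively sought. Related AEs, and AEs causing discontinuation, are followed beyond the study (Protocol 5.1.4, 9.2.3.5). SAE records are updated as new information arrives (Protocol 10.2). This stands: the loss falls mainly on AEs judged not related and is close to nil for short ones.
- **No duration statistic is named.** SAP Table 5.1 lists only subject numbers, percentages and event counts for safety. A duration table might carry a *Missing* row, as the onset table does (SAP 4.3.1.2.4). This stands too, but such a row would still not say that the events were ongoing.
- **Ongoing is a convention, not an observation.** An AE that resolved without its date being obtained also falls under the protocol footnote, so an absent stop date does not prove the minimum duration. This stands and shapes the fix.
- **No replacement of safety data** (Protocol 12.3.1, SAP 5.3.1). Reporting *at least x days* inserts no end date, so this is not a bar.
- **Outcome is summarised** (SAP 4.3.1.5.4). That may show events as unresolved, but not for how long.

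A reader might also infer more than the documents support:

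- *That the SAP contradicts the protocol on status.* It does not; it fails to carry the status into the derivation.
- *That only the longest events drop out.* This is a tendency; a short AE starting just before Visit 2 can be lost as well.
- *That the ongoing rule fails for pain, headache, malaise and myalgia because they have no measurement.* SAP 4.3.1.1.1 uses their recorded grades and provides for a maximum intensity after the solicited period.
- *That the share of solicited reactions still ongoing is biased low.* SAP 4.3.1.1.7 reads: "Missing: all other conditions (in this case, it is not included in the denominator of the ongoing analysis in the safety tables". A reaction graded on Day 7 with no later record may simply have ended that day, and excluding such cases would push the share up. The direction is not established.

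**Conclusion.** The point holds for unsolicited AEs, SAEs included. The protocol gives an absent stop date a meaning, and the SAP's duration rule does not use it. Any duration summary restricted to events with an end date tends to read short.

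Under the stated assumptions the effect ranges from negligible when AEs are short to more than a third of the mean when they average about two weeks and no late stop date is obtained (9.1 against 14.5 days). Recovering half of the late dates reduces the shortfall to roughly 0.5 days (7.0 against 7.5) and 2.3 days (12.2 against 14.5). The true size cannot be derived from the documents.

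For solicited reactions the issue is narrower. The listed endpoint, number of days of occurrence, is derived within Day 0 to Day 7 without an end date (SAP 4.3.1.1.5). Only the overall count in 4.3.1.1.6 is affected.

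AE occurrence is unaffected, and no hypothesis test or sample-size figure depends on this. It is a modest correction to a listed descriptive endpoint, worth making because it costs almost nothing.

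**What to change.** In SAP 4.3.1.2.5 and 5.3.1.4, and likewise in 4.3.1.1.6 for reactions continuing past Day 7:

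1. Separate two classes: *ongoing at last contact* and *end date partial or unknown*.
2. For the first class, report duration as at least (last contact − start + 1) days, with no imputed end date.
3. Show the number of ongoing events beside any duration summary.
4. Keep duration missing for events known to have resolved on an unknown or partial date. The outcome field that SAP 4.3.1.5.4 already expects can help identify them.
5. Define last contact. SAP 4.3.3.2 already uses the dates of last visit and termination. For a subject lost to follow-up, the last actual contact is the safer choice.

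**Cost.** A few lines of SAP text and a small extra derivation, with no new data collection. The downside is that an event which resolved without its date being obtained may be classed as ongoing and shown with too long a minimum. A footnote giving the protocol's convention would make that visible.

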4.3.1.3 Serious Adverse Events

An event will be considered as a serious event if “Yes” is checked for “Serious” in the CRF. SAEs will be analyzed throughout the study using the following periods:

- Within 7 days after vaccination
- Within 30 days after vaccination
- During the study (i.e., all SAEs occurred during the study)

4.3.1.4 Adverse Events of Special Interest

An event will be considered as an AESI if “Yes” is checked for “Is the event an AESI?” in the CRF.

AESIs will be analyzed throughout the study using the following periods:

- Within 7 days after vaccination
- Within 30 days after vaccination
- During the study (i.e., all SAEs occurred during the study)

4.3.1.5 Other Safety Endpoints

4.3.1.5.1 Pregnancy

This information will not be included in the analysis but will be listed separately. No derivation or imputation will be done.

4.3.1.5.2 Action Taken

This information will be summarized as collected, including missing observations. No derivation or imputation will be done.

4.3.1.5.3 Seriousness

This information will be summarized as collected for SAEs. No derivation or imputation will be done.

4.3.1.5.4 Outcome

This information will be summarized as collected for Unsolicited non-serious AEs and SAEs. No derivation or imputation will be done.

4.3.1.5.5 Causal relationship

This information will be summarized as collected in the field “Relationship to Investigational Product”. Missing causal relationship will be handled as described in [Section 5.3.1.2](#). Relationship to study procedure is only presented in the listing.

4.3.1.5.6 Adverse Events Leading to Study Discontinuation

This information will be summarized as collected. A flag is available in the clinical database for all AEs in order to identify AEs leading to discontinuation before the end of active phase.

In general, the items that are counted are:

- Disposition table: A subject who, on the “Completion at End of Study” form question “What was the participant's status?” has “Adverse Event” checked.
- Safety overview table: A participant who has either on the “Completion at End of Study” form, question “What was the participant's status?” has “Adverse Event” checked or lists a solicited AE that has “Caused Study Termination” checked that is at least Grade 1 or an unsolicited AE that has “Caused Study Discontinuation” checked that is at least Grade 1 or missing and is within the time period indicated.
- System Organ Class (SOC)/Preferred Term (PT) table: A solicited AE that has “Caused Study Termination” checked that is at least Grade 1 or an unsolicited AE that has “Caused Study Discontinuation” checked that is at least Grade 1 or missing and is within the time period indicated.

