5.1.3 Study Plan

Vaccination

All subjects will receive a single dose of MenACYW conjugate vaccine at Visit 1 (D0).

Blood sampling

All subjects will provide a pre-vaccination blood sample at Visit 1 and a post-vaccination sample at Visit 2 (30 to 44 days after the vaccination at Visit 1).

Collection of safety data

- All subjects will be followed for safety from Visit 1 (D0) to Visit 2.
- All subjects will be observed for 30 minutes after vaccination, and any unsolicited systemic AEs occurring during that time will be recorded as immediate unsolicited systemic AEs in the case report book (CRB).
- The subject will record information in a diary card about solicited reactions from D0 to D07 after vaccination and unsolicited AEs from D0 to Visit 2.

- SAEs (including AESIs) will be recorded throughout the duration of the trial. The subject will record information in a diary card about SAEs from D0 to Visit 2.
- The subject will be asked to notify the site immediately about any potential SAEs at any time during the trial.
- Staff will contact the subjects by telephone on D08 (+2 days) to identify the occurrence of any SAE not yet reported and to remind them to complete the diary card up to Visit 2 and to bring it back to Visit 2.
- The completed diary card will be reviewed with the subject at Visit 2.

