9.2.2 Safety Endpoints

The endpoints for the evaluation of safety are:

- Occurrence, nature (Medical Dictionary for Regulatory Activities [MedDRA] preferred term), duration, intensity, relationship to vaccination, and whether the event led to early termination from the study of any unsolicited systemic AEs reported in the 30 minutes after vaccination.
- Occurrence, time of onset, number of days of occurrence, intensity, action taken, and whether the reaction led to early termination from the study, of solicited (prelisted in the subject's diary card and electronic case report book [CRB]) injection site reactions occurring up to 7 days after vaccination.
- Occurrence, time of onset, number of days of occurrence, intensity, action taken, and whether the reaction led to early termination from the study, of solicited (prelisted in the subject's diary card and CRB) systemic reactions occurring up to 7 days after vaccination.
- Occurrence, nature (MedDRA preferred term), time of onset, duration, intensity, action taken, relationship to vaccination (for systemic AEs only), and whether the event led to early termination from the study, of unsolicited AEs occurring up to Visit 2.

- Occurrence, nature (MedDRA preferred term), time of onset, duration, seriousness criteria, relationship to vaccination, outcome, and whether the SAE led to early termination from the study, of SAEs (including AESIs) throughout the trial.

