4.3 Derived Endpoints: Calculation Methods

4.3.1 Safety

4.3.1.1 Solicited Reactions

4.3.1.1.1 Daily Intensity

All daily records for solicited reactions will be derived into daily intensity according to the following classification: None, Grade 1, Grade 2, Grade 3, or Missing (Unknown).

For the derivation of daily intensities the following sequential steps will be applied:

- 1) Solicited reactions (except Fever/Pyrexia) with CRF presence recorded as “No” and with all daily records missing (Unknown) then all daily intensities will be derived as None.
- 2) For non-measurable solicited reactions, daily intensities will correspond to daily records reported in the clinical database. For measurable solicited reactions the daily measurements reported in the clinical database will be converted based upon the intensity scales defined in the protocol; this assumes a reaction that is too large to measure (non measurable, “NM”) is Grade 3. Note the intensity could be considered “None” (not a reaction) in the analysis despite being considered a reaction by the investigator (e.g., swelling measurement > 0 mm but < 25 mm in adults).

Note: The maximum intensity on the ongoing period is derived from the record of the maximum intensity/measurement after the end of the solicited period following the rule described above.

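### SAP 4.3.1.5.6 counts an ungraded unsolicited AE that caused discontinuation but not an ungraded solicited reaction, so such a reaction has no row in the SOC/PT table

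*SAP*

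**What the plan says.** SAP 4.3.1.5.6 opens with a general statement: "This information will be summarized as collected. A flag is available in the clinical database for all AEs". It then defines three counts.

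- **Disposition.** This count rests on the end-of-study form and has no grade condition: "Disposition table: A subject who, on the “Completion at End of Study” form question".
- **Safety overview.** A subject counts if that form records an adverse event, or if a flagged event meets a grade test.
- **SOC/PT table.** Only flagged events count, subject to a grade test. For solicited reactions the test is "System Organ Class (SOC)/Preferred Term (PT) table: A solicited AE that has “Caused Study Termination” checked that is at least Grade 1". For unsolicited AEs the flag must be "checked that is at least Grade 1 or missing and is within the time period indicated".

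The overview bullet applies the same two grade tests as the SOC/PT bullet.

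SAP 4.3.1.1.1 gives the permitted daily intensities of a solicited reaction as "None, Grade 1, Grade 2, Grade 3, or Missing (Unknown"). Missing is thus a legitimate final value.

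Protocol 9.2.2 makes the link to discontinuation part of the safety endpoints. For systemic reactions the wording is "whether the reaction led to early termination from the study, of solicited (prelisted in the subject's diary card and CRB) systemic reactions", and injection site reactions have a parallel entry. SAP 4.2 repeats this.

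**The concern.** The two event types are asked the same question, whether the event ended the subject's participation, but face different tests. An ungraded unsolicited AE passes and an ungraded solicited reaction fails. The SAP gives no reason, and a filter on derived grade fits poorly with a promise to summarize the flag as collected.

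The missing grade may also be connected with the event being counted. Subjects enter daily solicited intensities on the diary card, and "The completed diary card will be reviewed with the subject at Visit 2". Someone who leaves in the first week because of a reaction is a plausible candidate for having no daily intensities.

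At stake is the preferred-term explanation of a discontinuation. Solicited reactions are treated as vaccine-related by convention (Protocol 9.2.3.5, SAP 5.3.1.2), so the absent row would be a related event. The SAP's other missing-data rules lean towards inclusion: missing causality counts as related (5.3.1.2), and unsolicited AEs with missing onset are kept (4.3.1.2.4, 5.3.1.4).

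**Working it through.** The plan states no figure to reproduce. The check is whether any other rule assigns a grade before the 4.3.1.5.6 filter applies, and then what the filter does.

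**Step 1. Can the grade stay missing?**

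- SAP 4.3.1.1.1 has one rule that resolves wholly missing records. It applies to reactions other than fever whose CRF presence is No, "and with all daily records missing (Unknown) then all daily intensities will be derived as None". A reaction that the investigator says ended participation would not normally carry presence No, so the rule does not reach it.
- SAP 4.3.1.1.2 takes the maximum of the daily intensities. If every day is missing, there is nothing to take a maximum of.
- SAP 4.3.1.1.3 turns a missing maximum into missing presence and leaves the subject out of that endpoint.
- SAP 5.3.1.3 refers back to 4.3.1.1.1 for solicited reactions and adds no grade.
- By contrast, SAP 4.3.1.2.1 accepts an unsolicited AE as an event if it has a verbatim term and is not Grade 0. A missing grade does not remove it.

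So the grade can stay missing, and nothing upstream of 4.3.1.5.6 repairs it.

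**Step 2. Apply the counting rules to an event with its termination or discontinuation flag checked** (for unsolicited AEs, within the stated period).

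| Event and grade | SOC/PT table | Overview, form says adverse event | Overview, form gives another reason |
|---|---|---|---|
| Solicited, missing | not counted | counted | not counted |
| Solicited, None | not counted | counted | not counted |
| Solicited, Grade 1 to 3 | counted | counted | counted |
| Unsolicited, missing | counted | counted | counted |
| Unsolicited, Grade 0 | not counted | counted | not counted |
| Unsolicited, Grade 1 to 3 | counted | counted | counted |

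The two event types differ only in the missing-grade rows. They differ in the SOC/PT column and in the last overview column.

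**Step 3. Scale, for illustration.** Inputs: 290 enrolled (SAP 5.7.2); assumed, all 290 in the safety set and exactly one such subject. Exact (Clopper-Pearson) 95% limits:

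- 0/290: upper limit 1 − 0.025^(1/290) = 1.26%, so 0 to 1.26%.
- 1/290 = 0.34%: lower limit 1 − 0.975^(1/290) = 0.01%; upper limit is the 97.5% point of Beta(2, 289) = 1.91%.

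Under that assumption the SOC/PT table would show the first line where the second is right.

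**The case against.** The best defence is that the case hardly arises. Protocol 5.1.4 requires an AE that caused discontinuation to be followed until it resolves, stabilizes or becomes chronic. Protocol 5.2.12 has the site contact subjects who stopped because of an AE. Protocol 13.2 provides for verbal clarification of missing diary data, and Protocol 9.2.1 makes the investigator's assessment of solicited reactions mandatory. One graded day is enough to produce a maximum intensity. To be lost, a reaction needs presence other than No, no intensity on any day, and the termination box checked. This stands: the diary is not the only route to a grade, and a wholly ungraded reaction should be uncommon. It narrows the gap without closing it.

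It can also be said that the subject is not lost. Protocol 5.2.9 and 5.2.11 direct the site to record an adverse event as the reason where safety led to withdrawal, and that entry alone puts the subject in the disposition and overview tables. This stands too. A reader might infer that the rule makes the overall discontinuation rate look better than observed. The documents do not support that in the usual case: what is lost is the preferred-term row. The overview loses the subject only if the form and the event flag disagree.

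A reader might add a second leak: a redness or swelling under 25 mm that the investigator blamed for the termination. That is not an asymmetry. SAP 4.3.1.1.1 and 4.3.1.2.2 declare the same convention for both event types, and SAP 4.3.1.2.1 sends Grade 0 unsolicited events to listings. Counting solicited events whatever their derived grade would create a new inconsistency.

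Finally, the difference may be a convention carried over from the general presence rules, and the SAP introduces the bullets as applying in general. That may explain its origin but does not justify it for this endpoint.

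**Conclusion.** The point holds in a narrow form and is minor. As written, the SOC/PT table omits a flagged solicited reaction of missing grade while it would include a flagged unsolicited AE of missing grade. The overview omits it as well when the Completion form gives another reason. No other SAP rule closes the gap.

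The number of such cases is not given and may be zero. The 1/290 illustration rests on one assumed case and on a safety set equal to the 290 enrolled. The trial is single-arm and descriptive, so no comparison or test is affected.

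A reader might also expect the SOC/PT total to agree with the Completion form once the rule is changed. That does not follow. The form records one most significant reason per subject, whereas the SOC/PT table uses event-level flags and, for unsolicited AEs, a time period. One subject may have several flagged events, or one outside the period.

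**What to change.** In the safety overview and SOC/PT bullets of SAP 4.3.1.5.6, let the solicited arm count a reaction with the termination box checked when its grade is at least 1 or missing, as the unsolicited arm already does. Add that any flagged solicited reaction with derived grade None is listed separately and not counted, in line with the treatment of Grade 0 unsolicited events.

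The cost is a few words in the SAP, one filter in the table program and a short listing. No new data are needed. The SOC/PT discontinuation count may become slightly less favourable.
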